6.3.23 Medication Diary for Arm A Participants

At the weeks before the PK assessment, a medication diary will be given to **participants** and collected from **participants** at the PK visits as indicated in section 6.1. **Participants** will be instructed to record the date and time they took their ruxolitinib and their ARV medications for the 3 days preceding the PK study visit.

6.3.24 Adherence Assessment

Self-reported adherence for ruxolitinib and ARV will be performed at the indicated visits per section 6.1.

7.0 CLINICAL MANAGEMENT ISSUES

7.1 Toxicity

Only toxicities related to the study **drug**, (ruxolitinib,) will be considered in the toxicity management section. The grading system is located in the Division of AIDS Table for Grading the Severity of Adult and Pediatric Adverse Events (DAIDS AE Grading Table), Version **2**.0, **November 2014**, located at the DAIDS R**S**C Web Site: http://rsc.tech-res.com/safetyandpharmacovigilance/

NOTE: The study core team must be notified by e-mail regarding toxicities that result in a change in regimen or discontinuation of study treatment ([contact]).

7.1.1 Grade 1 or 2

Participants who develop a Grade 1 or 2 AE or toxicity may continue study drug without alteration of the dosage, except as stated in sections 7.2.1 to 7.2.8. For **participants** experiencing Grade 1 or 2 AEs who choose to discontinue study drug, the site investigator should complete premature treatment discontinuation evaluations, and the **participant** should be encouraged to complete evaluations off treatment/on study.

NOTE: If **participants** discontinue study drug due to experiencing Grade 1 or 2 AEs, this should be noted in the CRF as the reason for discontinuation.

7.1.2 Grade 3

Participants who develop a Grade 3 AE thought to be related to the study drug should have their study medication **discontinued**. If the investigator has evidence that the AE has NOT been caused by study drug, study drug should be held until the AE or clinically significant laboratory abnormality is Grade ≤ 1 in severity, except as stated in sections 7.2.1 to 7.2.8 below.

If the same Grade 3 AE recurs at any time within 3 weeks after restarting treatment, the study drug must be permanently discontinued.

Participants experiencing Grade 3 AEs requiring permanent discontinuation of study drug should be followed weekly until resolution of the AE and should complete the premature treatment discontinuation evaluations and should be encouraged to complete off treatment/on study evaluations.

7.1.3 Grade 4

Participants who develop a Grade 4 symptomatic AE will have study drug permanently discontinued, except as stated in sections 7.2.1-7.2.8 below. **Participants** experiencing Grade 4 AEs requiring permanent discontinuation of study **drug** should be followed weekly until resolution of the AE and should complete the premature treatment discontinuation evaluations and the

participant should be encouraged to complete off treatment/on study evaluations.

7.2 Other Toxicities

- 7.2.1 Platelet Count Reductions
 - 7.2.1.1 If a **participant** develops a platelet count decrease of >25% from baseline with an absolute value remaining above 200,000/mm³, then dosing can continue.
 - 7.2.1.2 If the platelet count decreases from baseline by ≥ 25%, and the absolute value is between 150,000-200,000/mm³, then dosing of the study drug should be reduced to 10 mg QD. The CBC should then be repeated weekly until the platelet count either returns to > 200,000/mm³ or remains less than 10% below the value that led to the dose reduction for two consecutive values. If the platelet count returns > 200,000/mm³, and is > 1.10 times the value that led to the dose reduction, then BID study drug dosing can resume. The **participant** will then have weekly monitoring until the platelet count remains at a value that is greater than the value at BID dose resumption for at least two consecutive values. After resumption of the BID dosing if the platelet count decreases to < 200,000/mm³, then the dose will be decreased to 10 mg daily and remain at that dose except as noted in section 7.2.3.
 - 7.2.1.3 If the platelet count decreases by ≥ 25%, and an absolute value below 150,000/mm³, then the study drug should be discontinued. The CBC should then be repeated weekly until the platelet count returns to > 150,000/mm³.

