4.1.5 **Tuberculosis (TB) screening within 365 days of the screening visit diagnosed by tuberculin skin test or interferon gamma release assay.**

4.1.6 Currently on continuous ART for at least 730 days prior to study entry, defined as continuous ART for the 730 days period, inclusive, prior to study entry with no ART interruption longer than 7 consecutive days.

NOTE: The current regimen must include tenofovir/emtricitabine (TDF/FTC) or abacavir/lamivudine (ABC/3TC) + a nonnucleoside reverse transcriptase inhibitor or integrase strand transfer inhibitor (NNRTI or INSTI, not containing cobicistat) for at least 60 days, inclusive, prior to study entry.

- 4.1.7 The following laboratory values obtained \leq 30 days prior to entry by any US laboratory that has a CLIA certification or its equivalent:
 - Absolute neutrophil count (ANC) ≥ **1000**/mm³
 - Hemoglobin ≥ 12.0 g/dL
 - Platelets ≥ 200,000/mm³
 - Calculated creatinine clearance (CrCl) ≥ 80 mL/min (by Cockcroft Gault equation). NOTE: A calculator for estimating the CrCl can be found at www.fstrf.org/ACTG/ccc.html
 - Aspartate aminotransferase (AST) (SGOT) ≤ 1.5x ULN
 - Alanine aminotransferase (ALT) (SGPT) ≤ **1.5**x ULN
 - Alkaline phosphatase ≤ **1.5**x ULN
- 4.1.8 For females of reproductive potential (defined as women who have not been post-menopausal for at least 24 consecutive months, i.e., who have had menses within the preceding 24 months, or women who have not undergone surgical sterilization, specifically hysterectomy and/or bilateral oophorectomy or bilateral salpingectomy) must have a negative serum or urine pregnancy test with a sensitivity of 25 mIU/mL within 72 hours, inclusive, prior to study entry.
- 4.1.9 All **participants** must agree not to participate in a conception process (e.g., active attempt to become pregnant or to impregnate, sperm donation, in vitro fertilization).
- 4.1.10 All **participants** of reproductive potential, who are participating in sexual activity that could lead to pregnancy, must agree to use at least one reliable method of contraception while receiving the study drugs and for 7 weeks after stopping the medications. Acceptable forms of contraceptive include:
 - Condoms (male or female) with or without a spermicidal agent
 - Diaphragm or cervical cap with spermicide

- Intrauterine device (IUD)
- Hormone-based contraceptive (must contain at least 35 mcg of ethinyl estradiol)

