7.2.3 Creatinine Clearance

Any **participant** experiencing a calculated CrCl < **60** mL/min should have the value confirmed within 7 days. For those **participants** who experience a confirmed (2 consecutive) CrCl < **60** mL/min, study drug should be withheld. If the site investigator determines that another condition caused the decrease in CrCl, then study drug may be restarted if approved by the protocol team. **Participants** should be followed as medically indicated until the serum creatinine

returns to Grade ≤ 2 or baseline.

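### After BID dosing resumes, the platelet rule names only the creatinine section as an exception, so read literally it conflicts with the platelet stop rule

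*Protocol*

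**What the plan says.** Protocol 7.2.1 contains three numbered platelet rules.

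- **7.2.1.1** covers a fall of more than 25% from baseline "with an absolute value remaining above 200,000/mm³, then dosing can continue".
- **7.2.1.2** covers a fall of at least 25% "and the absolute value is between 150,000-200,000/mm³, then dosing of the study drug should be reduced to 10 mg QD". It lets BID dosing resume once the count is above 200,000/mm³ and more than 1.10 times the value that triggered the reduction. It then adds a rule for any later drop under 200,000/mm³ once BID dosing is back: "then the dose will be decreased to 10 mg daily and remain at that dose except as noted in section 7.2.3".
- **7.2.1.3** is the stop rule: a fall of at least 25% "and an absolute value below 150,000/mm³, then the study drug should be discontinued".

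The section named as the exception is headed "7.2.3 Creatinine Clearance". It covers confirmed low creatinine clearance and contains no platelet instruction.

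Three other places bear on the point. Entry requires "Platelets ≥ 200,000/mm³" within the 30 days before entry (Protocol 4.1.7). Section 7.1.1 lets a participant with a Grade 1 or 2 toxicity continue at an unchanged dose unless 7.2.1 to 7.2.8 say otherwise. Stopping ruxolitinib because of thrombocytopenia is a component of the primary safety outcome (Protocol 9.2.1.1; SAP 2.4.1, outcome 1), and premature treatment discontinuation is the tolerability outcome (Protocol 9.2.1.2; SAP 2.4.1, outcome 4).

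**The concern.** A rule that names one exception is naturally read as allowing no others. Here the named exception has nothing to do with platelets, and the platelet stop rule next to it is left out. A site following 7.2.1.2 to the letter would keep a participant on 10 mg daily at a count where 7.2.1.3 says to discontinue.

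Thrombocytopenia is among the most common adverse events the protocol reports for this drug (Protocol 2.2), and the action the site takes is itself counted as an outcome. Two sites facing the same count could act differently. One would record a primary safety event and a premature discontinuation, and the other would record neither.

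**Working it through.** The protocol states no figure to reproduce. The check is to write each rule as a condition and see which ones apply. Let B be the baseline count and c the current count, with fall f = (B - c)/B.

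| Rule | Condition | Instruction |
|---|---|---|
| 7.2.1.1 | f > 25% and c > 200,000 | dosing can continue |
| 7.2.1.2, first reduction | f ≥ 25% and c from 150,000 to 200,000 | 10 mg once daily |
| 7.2.1.2, after BID resumption | c < 200,000; no condition on f, no lower bound | 10 mg daily and remain, except per 7.2.3 |
| 7.2.1.3 | f ≥ 25% and c < 150,000 | discontinue |

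**Where two instructions apply.** For B ≥ 200,000, 0.75 × B is at least 150,000. Any c below 150,000 is therefore a fall of more than 25% and meets 7.2.1.3. After resumption the same c is below 200,000 and also meets the 7.2.1.2 sentence. The two rules overlap at every count below 150,000.

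**A path that reaches the overlap (illustrative counts, B = 260,000).**
1. The count drops to 180,000. f = 80/260 = 30.8%, so the first reduction applies.
2. The count recovers to 205,000. This is above 200,000 and above 1.10 × 180,000 = 198,000, so BID dosing can resume.
3. The count drops to 140,000. f = 120/260 = 46.2%. The 7.2.1.2 sentence says 10 mg daily and remain; 7.2.1.3 says discontinue.

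**Effect on the outcomes.** Arm A has 40 participants. If stopping for thrombocytopenia is the only milestone a participant meets, handling that one participant one way or the other moves the ruxolitinib-arm proportion by 1/40 = 2.5 percentage points. The between-arm comparison replaces this component with Grade 2 or higher thrombocytopenia (Protocol 9.6.1; SAP 2.4.1, outcome 2, tested under SAP 4.1.1). That is defined by the count and not by the action taken, so the comparison does not depend on which instruction a site follows.

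**Secondary check: first falls of under 25%.** Before any reduction, a count above 0.75 × B and no higher than 200,000 meets none of the three rules. This needs 0.75 × B < 200,000, so B < 200,000/0.75 = 266,667.

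| Baseline | Counts that meet no numbered platelet rule |
|---|---|
| 200,000 | above 150,000, up to 200,000 |
| 220,000 | above 165,000, up to 200,000 |
| 240,000 | above 180,000, up to 200,000 |
| 266,667 or more | none |

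After resumption the 7.2.1.2 sentence covers this band, apart from a count of exactly 200,000. Below 150,000 there is no such gap for B ≥ 200,000, because the stop rule then always applies.

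**The case against.** The best defence is that the conflict comes from one wrong section number and is hard to reach. A participant must be reduced, recover past both thresholds, resume BID dosing and then drop below 150,000, and treatment lasts only 5 weeks. Protocol 2.2 describes the average platelet change at 10 mg BID as negligible. Section 7.2.1.3 carries no condition on dosing history, so it can be read as still in force, and the instruction to stay on the lower dose can be read as only ruling out another return to BID. All of this bears on how often the problem would arise and how a careful site might resolve it. It does not change what the text says, and the text makes the site choose.

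Three stronger readings are tempting, and the documents do not support them.

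- *Counts of 150,000-200,000 with a fall of under 25% are outside every rule.* They are outside the numbered platelet rules only before a first reduction and only for baselines below about 266,667. Continuation is implied by 7.1.1 if the count is Grade 1 or 2, or by the assigned regimen in 5.1 if it is not graded. The documents do not reproduce the grading table, so which route applies cannot be settled here.
- *The rules treat like counts inconsistently.* Any percentage criterion handles equal counts differently by baseline, and a stricter rule after an earlier reduction may be deliberate.
- *The gap feeds the conflict, or affects a known large share of Arm A.* The conflict arises from the cross-reference and the missing lower bound; the gap plays no part. Any percentage would need the mean, spread and within-person variation of entry platelet counts, and the documents give none of these.

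**Conclusion.** The point holds in a narrow form. Protocol 7.2.1.2 refers to a section without platelet content and does not except 7.2.1.3. For any count below 150,000/mm³ after BID resumption, the two passages therefore literally give different instructions. The ruxolitinib-arm safety proportion and the tolerability outcome are exposed; the between-arm safety test is not. The number of participants affected cannot be estimated from the documents and is probably small. The reason to act is that this is a dosing instruction tied to a primary outcome and is easily corrected.

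The silence on a first fall of under 25% to 150,000-200,000 is a lesser matter of clarity. It could at most lead to a disputed dose reduction, because the stop rule itself has no gap.

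Two assumptions apply. The overlap and the absence of a gap in the stop rule assume a baseline of at least 200,000, which is the eligibility threshold. The reading is of Protocol Version 2.0 as supplied; a later clarification may exist.

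**What to change.** Correct the cross-reference in 7.2.1.2 and reconcile that sentence with 7.2.1.3, so that every platelet count after BID resumption has exactly one instruction. The clinical team decides what that instruction is. In the same document, have the clinical team state what is intended for a first fall of under 25% to a count of 150,000-200,000, instead of leaving it to inference from 7.1.1 or 5.1.

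A clarification memo or short letter of amendment is enough. There is no effect on sample size, power or the planned tests. If dosing is already complete, the analysis report should list any participant whose count dropped below 150,000 after BID resumption and say which instruction the site followed.

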7.2.2 Anemia/Neutropenia

If a **participant** experiences treatment-limiting **Grade 3 or higher decrease** (in the opinion of the site investigator) **in** anemia or neutropenia, then study drug should be withheld. **A**nemia **should not** be managed by transfusions **or** recombinant erythropoietin, and neutropenia **should not** be managed with granulocyte-colony stimulating factor (G-CSF) or granulocyte-macrophage colony-stimulating factor (GM-CSF). Once the anemia or neutropenia has returned to Grade \leq 2, the study drug can be restarted.

7.2.3 Creatinine Clearance

Any **participant** experiencing a calculated CrCl < **60** mL/min should have the value confirmed within 7 days. For those **participants** who experience a confirmed (2 consecutive) CrCl < **60** mL/min, study drug should be withheld. If the site investigator determines that another condition caused the decrease in CrCl, then study drug may be restarted if approved by the protocol team. **Participants** should be followed as medically indicated until the serum creatinine

returns to Grade ≤ 2 or baseline.

7.2.4 Bruising and Bleeding

For participants who report generalized bruising and/or symptoms of unexplained or abnormal bleeding, hematoma or epistaxis, the study drug should be discontinued.

7.2.5 Nausea (with or without vomiting) and/or Diarrhea

With the onset of Grade \geq 1 nausea advise **participants** to take study drug with food. **Participants** may also be treated as needed with antiemetics given PO or by suppository.

In **participants** with persistent nausea, consideration should be given for evaluation of pancreatitis, hepatitis, or hyperlactatemia/lactic acidosis, with evaluation for each if clinically indicated.

For Grade 1 or 2 diarrhea, therapy should be continued with symptomatic treatment with antimotility agents. If Grade \geq 3 diarrhea occurs and is unresponsive to antimotility agents, and for which an alternative etiology (e.g., infectious diarrhea) is not established **and judged related to study drug**, study drug should be withheld until resolution of diarrhea to Grade \leq 1 or return to baseline. If Grade \geq 3 diarrhea recurs upon the resumption of the study drug, study drug should be discontinued.

7.2.6 Hypertriglyceridemia/Hyperlipidemia

If elevated triglyceride or lipid levels are from a non-fasting blood draw, repeat the draw after an 8-hour fast. Only levels done in a fasting state should be used to determine toxicity management. **Participants** with asymptomatic Grade 3 **or higher increases in** triglyceride, total cholesterol, or LDL elevations **must dis**continue study drug. Please see the recent review adapted from the original recommendations of the ACTG Cardiovascular Disease Focus Group (http://www.ncbi.nlm.nih.gov/pmc/articles/PMC2753589) for full discussion of management of hyperlipidemia in the context of HIV-1 disease.

7.2.7 Hyperglycemia

Participants with Grade 3 or higher hyperglycemia must discontinue their study drug unless judged unrelated to the study drug. If judged unrelated, study drug must be held until the glucose abnormalities are Grade \leq 1. Oral hypoglycemic and insulin should not be used in order to allow continued study drug administration. A confirmatory fasting glucose must be obtained within 2 weeks and prior to the institution of medical therapy.

7.2.8 AST or ALT Elevations

Study **drug must** be **dis**continued for asymptomatic Grade 3 **or higher** AST/ALT elevations **unless judged unrelated to study drug**. Careful assessments should be done to rule out the use of alcohol, non-study drug-related drug toxicity, or viral hepatitis as the cause of Grade 3 elevations. **If judged unrelated, s**tudy drug should be held **until AST and/or ALT levels are Grade ≤ 1.**

7.3 Other Diseases

For unexplained confusion, seizures, or other CNS abnormality site investigators should assess the **participant**, in conjunction with the primary physician to determine the cause of the symptoms. If no cause can be identified, or other physician suspects PML, then study drug should be discontinued. The **participant** should then be followed on study until another cause is established, or PML is considered confirmed or probable according to criteria in Appendix 100, ACTG Criteria for Clinical and Other Events. For any infection, site investigators should assess the **participant**, in conjunction with the primary physician to determine relatedness to the study drug. If the infection is considered related to the study drug, then the study drug should be discontinued.

7.4 Pregnancy

Female **participants** who become pregnant while on study treatment must immediately discontinue study treatment. **Participants** should have the Premature Treatment/Study Discontinuation Evaluations completed within 2 weeks after stopping study treatment. Pregnancies that occur on study should be reported prospectively to The Antiretroviral Pregnancy Registry. More information is available at www.apregistry.com. [contact]; [contact].

Participants will be encouraged to remain in the study to be followed on study/off study treatment until study completion and will be followed by telephone contact thereafter to determine the pregnancy outcome. If a **participant** does not wish to remain on study follow-up at the time of study discontinuation, site staff should request permission to contact her regarding pregnancy and infancy outcomes at the end of the pregnancy. If the information is obtained, pregnancy outcomes for the **participant** and infant will be submitted on a CRF at the end of pregnancy.

7.5 Confirmed Virologic Failure

In the event of confirmed virologic failure, defined as the occurrence of two sequential plasma HIV-1 RNA values above the lower limit of quantification in the absence of an interruption in ART, the study drug must be stopped for participants in Arm A. The participant will be followed on study with all evaluations performed through week 12. If the participant does not agree to continue on study, then the premature study discontinuation evaluations should be completed.

8.0 CRITERIA FOR DISCONTINUATION

- 8.1 Premature Treatment Discontinuation
 - Drug-related toxicity (see section 7.1 Toxicity).
 - Requirement for prohibited concomitant medications (see section 5.4).
 - Changes to or discontinuation of ART for Arm A participants.
 - **Participant** repeatedly noncompliant (missing greater than 3 doses of study drug a week for 2 or more weeks).
 - Confirmation of virologic failure (see section 7.5).
 - Pregnancy or breastfeeding.
 - Request by **participant** to terminate treatment.
 - Clinical reasons believed life threatening by the physician, even if not addressed in the toxicity section of the protocol.
- 8.2 Premature Study Discontinuation
 - Failure by the **participant** to attend 2 consecutive clinic visits.
 - Request by the participant to withdraw.
 - Request of the primary care provider if s/he thinks the study is no longer in the best interest of the **participant**.
 - **Participant** judged by the investigator to be at significant risk of failing to comply with the provisions of the protocol as to cause harm to self or seriously interfere with the validity of the study results.
 - At the discretion of the Institutional Review Board/Ethics Committee (IRB/EC), FDA, NIAID, Office for Human Research Protections (OHRP), other government agencies as part of their duties, or the investigator.

9.0 STATISTICAL CONSIDERATIONS

9.1 General Design Issues

A5336 is a randomized (2:1), prospective, open-label, 2-arm pilot clinical trial designed to assess the safety and tolerability of ruxolitinib, and to evaluate whether 5 weeks of treatment with ruxolitinib decreases IL-6 levels in HIV-1 infected **participants** virally suppressed on ART. **Participants** will be randomized 2:1 to receive ruxolitinib or no study treatment. **Participants** receiving ruxolitinib will be followed on treatment for 5 weeks, then for an additional 7 weeks off treatment, resulting in a total 12 weeks of follow-up; **participants** receiving no study treatment will be followed on-study for 12 weeks. The total sample size will be 60 **participants**.

- 9.2 Objectives
 - 9.2.1 Primary Outcome Measures
 - 9.2.1.1 Safety

Occurrence of any one of the following safety milestones (from entry to week 5).

- For **participants** with entry CD4+ T cell count < 700 cells/mm³, confirmed CD4+ decline > 33% of baseline and to < 350 cells/mm³.
- For **participants** with entry CD4+ T cell count ≥ 700 cells/mm³, a confirmed CD4+ T cell decline > 50 % of baseline.
- Confirmed HIV-1 RNA level **above the lower limit of quantification** in the absence of an interruption in ART.
- New or recurrent CDC category C AIDS-indicator condition.
- HIV-1 associated infection including Varicella zoster.
- Lymphoproliferative malignancies.
- Discontinuation of ruxolitinib due to thrombocytopenia.
- Grade 4 or recurrence of Grade 3 anemia/neutropenia.
- Any Grade 4 or recurrence of Grade 3 toxicity related to study drug.
- New diagnosis of pneumonia, sepsis, or bacteremia.
- 9.2.1.2 Tolerability
 - Occurrence of premature discontinuation of study treatment.
- 9.2.1.3 IL-6

Participant-specific change in the level of plasma IL-6 (using geometric means of two ELISA measurements at pre-entry and entry, and weeks 4 and 5).

- 9.2.2 Secondary Objective Measures
 - 9.2.2.1 Proportion of **participants** who experienced any one of the primary safety milestones during total follow-up (from entry to week 12).
 - 9.2.2.2 Summary of safety laboratories at baseline and weeks 1, 2, 4, 5, 10, and 12.
 - 9.2.2.3 Change in the level of plasma IL-6 from baseline to weeks 4, 5, 10, and 12.
 - 9.2.2.4 Changes in soluble markers of immune activation and inflammation in the peripheral blood (sCD14, TNF- α , IL-1 α , IL-1 β , mCSF, and neopterin) from baseline to weeks 4, 5, and 12.

- 9.2.2.5 Changes in cellular markers of immune activation and inflammation in the peripheral blood (HLA-DR, CD38, CD69 and CD14+/CD16+ monocyte levels) from baseline to weeks 5 and 12.
- 9.2.2.6 Changes in plasma HIV-1 RNA and CD4+ T cell counts from baseline to weeks 2, 5, and 12.
- 9.2.2.7 Changes in HIV-1 reservoir (HIV-1 RNA by SCA, cellular HIV-1 total RNA and DNA, 2-LTRs, integrated DNA) from baseline to weeks 5 and 12.

9.2.2.8 Level of HHV shedding (CMV, EBV, HHV 6, 7, 8) at pre-entry, entry, and weeks 1, 2, 4, 5, 10, and 12.

